**Document Date:**

**January 14, 2022**

## I. BACKGROUND AND SIGNIFICANCE

### 1. Why Nondaily Smoking Matters

Cigarette smoking continues to be the leading cause of preventable disease and death in the United States, accounting for more than 480,000 deaths every year. While the prevalence of smoking has steadily declined over a number of years, an increasingly prevalent pattern of smoking is nondaily smoking. Currently, 24.3% of all adult smokers are nondaily smokers, which constitutes a 27% increase in prevalence in the last decade.

Nondaily smoking poses substantial health risks, and is a recognized public health issue. It poses significant carcinogenic exposure (i.e., 40-50% of that seen in daily smokers) and has been linked to total and cardiovascular mortality among men. Indeed, the risk for cardiovascular disease has been found to be nearly equal to that of daily smoking, given a highly non-linear dose-response relationship between tobacco exposure and cardiovascular mortality.

**Untreated nondaily smoking contributes to persisting health disparities** in smoking prevalence. Nondaily smoking is disproportionately represented in ethnic minority groups, and increasingly prevalent in adults with a mental health or substance use problem. Both of these groups have substantially higher smoking prevalence rates (e.g., 31.8% in American Indian/Alaska Natives, 35.8% in adults with serious psychological distress, 65% to 87% in individuals with substance use disorders) compared to the general population (15.5%). Thus, a failure to provide smoking cessation support for nondaily smokers disproportionately impacts populations already systematically missed by current public health efforts.

### 2. The Need for Smoking Cessation Support for Nondaily Smokers

Nondaily smokers are motivated to quit smoking. Indeed, epidemiological evidence demonstrates that compared to daily smokers, nondaily smokers have greater current intentions to quit smoking, and more recent and planned cessation efforts than daily smokers. The fact that nondaily smokers regularly abstain from smoking from day-to-day suggests that they should have relatively little trouble quitting, but recent evidence demonstrates that most nondaily smokers (up to 82%) fail in their quit attempts. Together, the high motivation to quit coupled with a high failure rate demonstrate the need for smoking cessation support for nondaily smokers.

### 3. Why Traditional Smoking Cessation Interventions Fail Nondaily Smokers

Engaging nondaily smokers in treatment has been largely unsuccessful. Despite being motivated to quit, nondaily smokers are less likely than heavier smokers to seek or receive treatment, leaving cessation efforts among nondaily smokers largely unaided. Treatment engagement is made difficult by nondaily smokers' resistance to being thought of as smokers: nondaily smokers feel less addicted than daily smokers, do not consider themselves to be smokers, and will deny their smoking habit when asked by family, friends, and healthcare providers. In line with these self-perceptions are data from cross-sectional, naturalistic and laboratory studies that show that nondaily smokers differ from daily smokers on important dimensions related to smoking cessation, including lower levels of dependence, higher levels of self-control, superior smoking-related error processing on neurocognitive tasks, and lower sensation-seeking impulses.

One reason traditional smoking cessation treatments fail to appeal to nondaily smokers may be that they are simply not applicable. Existing treatments for smoking cessation are based on studies of daily smokers, and theoretical models of cigarette smoking assume daily smoking.

Such models posit that smoking is primarily driven by nicotine dependence, such that smokers smoke in order to maintain nicotine levels above a certain level, thereby preventing the occurrence of withdrawal symptoms. Nondaily smokers, however, do not smoke continuously. Rather, they smoke on average 4 days per week, and 4 cigarettes per smoking day, and thus are not maintaining a specific level of nicotine. Their reasons for smoking also tend to be different, when compared to daily smokers. Nondaily smokers tend to smoke for social enhancement rather than to cope with negative affect, and tend to be driven by acute, situational motives (e.g., cue exposure, positive reinforcement) rather than nicotine dependence (e.g., tolerance, withdrawal symptoms). These data suggest that **treatments emphasizing withdrawal and dependence are likely inappropriate for nondaily smokers.**

#### 4. Smiling Instead of Smoking

We developed a smartphone app that specifically addresses the characteristics of nondaily smoking. To support smoking cessation, we use a positive psychology approach. Positive affect enhancement is an empirically sound treatment target: positive affect is psychometrically and neurologically distinct from negative affect, and plays an important role in the days leading up to and following a quit attempt. Enhancing positive affect with brief, self-administered exercises is entirely feasible: in recent years, a large number of positive psychology exercises have been developed that have consistently led to improvements in happiness, reductions in depression, and improvements in overall well-being. Our smartphone app, “Smiling instead of Smoking” administers such positive psychology exercises to enhance and/or maintain positive affect, which is hypothesized to stimulate nondaily smokers to enact healthier alternatives to smoking by broadening their thought-action repertoire, increasing confidence, and decreasing craving and defensiveness about smoking-related health information (Figure 1).

[figure not shown]

Figure 1. Theorized Mechanisms of Behavior Change

The focus on happiness will help overcome treatment resistance, as the pursuit of happiness is generally appealing and non-stigmatizing. To this end, we have worked closely with nondaily

smokers in Study 1 (#2017P001106) and Study 2 (#2018P002699) to develop Version 3.0 of our “Smiling Instead of Smoking” app. In the current study (i.e., Study 3 in a series of 3 studies funded by the American Cancer Society (130323-RSG-17-021-01-CPPB)), we will conduct a proof-of-concept RCT of Version 3.0 of this app.

## II. SPECIFIC AIMS

This is the third study in a series of 3 studies to develop a smartphone app to support nondaily smokers in quitting smoking, as funded by the American Cancer Society grant #RSG CPPB – 130323 (project dates: 07/01/2017 – 6/30/2021). Study 1 (2017P001106) demonstrated feasibility and acceptability when smokers were onboarded in person. Study 2 (2018P002699) demonstrated feasibility and acceptability when smokers were onboarded remotely, nationwide. The present study is Study 3. It is a 3-group proof-of-concept RCT, in which we seek to test if our app (i.e., Version 3 of our developed smartphone app, called ‘Smiling instead of Smoking’ (SiS)) is superior to treatment as usual (i.e., TAU; no treatment for nondaily smokers) and superior to a control app (i.e., the National Cancer Institute’s smartphone app “QuitGuide” (QG). Specifically, our aims are to:

1. Test for differences between randomized groups on the primary outcome of this proof-of-concept RCT, as measured at end of treatment (i.e., Week 6 post-quit): Self-efficacy to remain abstinent, as measured via the Smoking Self-Efficacy Questionnaire (SEQ): two-dimensional 12-item self-report scale measuring a person’s confidence in his or her ability to abstain from smoking when facing internal stimuli [e.g. feeling depressed] and external stimuli [e.g. being with smokers]. Participants rate each item on a sliding scale from 0 [not at all confident] to 100 [extremely confident]. Two subscale scores are created by averaging items assessing internal vs. external stimuli, respectively. We hypothesize that SiS > QG > TAU.
2. Test for differences between randomized groups on secondary outcomes:
  - a. Self-reported 30-day point-prevalence abstinence 6, 12 and 24 weeks post quit. We hypothesize that SiS > QG > TAU.
  - b. Self-reported past week cigarette reduction at 2, 6, 12, and 24 weeks post quit, compared to baseline. We hypothesize that SiS > QG > TAU.
  - c. Satisfaction with smoking cessation support, as self-rated on the Client Satisfaction Questionnaire (CSQ-8) at end of treatment. We hypothesize that SiS > QG > TAU.
  - d. Time spent applying content brought up by the apps/”Clearing the Air” at end of treatment (“During this past week, how much time did you spend applying or contemplating the content of the SiS app/QG app/”Clearing the Air”?” [in minutes]). We hypothesize that SiS > QG > TAU.
  - e. Use of smoking cessation strategies, as assessed at end of treatment. We hypothesize that SiS > QG > TAU.
  - f. Perceived impact of the provided materials on quitting (e.g., “reminded me to stay on track”), as assessed at end of treatment. We hypothesize that SiS > QG > TAU.
  - g. Appreciation, as measured via the Appreciation Scale at end of treatment. The Appreciation Scale is an 18-item scale which assesses the degree to which one is appreciative. This is an important process outcome for this study, as the SiS app,

unlike the QG app or TAU, emphasizes the experience of positive emotions in order to support smoking cessation. Ten of the items assess frequency of action (e.g., “I do things to remind myself to be thankful” 7-point Likert: 1 = More than once a day, 2 = About once a day, 3 = About once a week, 4 = About once a month, 5 = About once a year, 6 = A few times in my life, 7 = Never). The remaining eight of the items assess level of agreement with appreciative statements (e.g., “I feel that it is a miracle to be alive” 7-point Likert: 1 = Strongly agree, 2 = Agree, 3 = Agree somewhat, 4 = Neither agree nor disagree, 5 = Disagree somewhat, 6 = Disagree, 7 = Strongly disagree). We hypothesize that SiS > QG > TAU.

- h. *(SiS and QG only)* Actual app usage – number of days participants used the assigned app during the prescribed period of app use (i.e., 7 weeks for both apps). Please note that we have a partnership agreement in place with the National Cancer Institute (see attached email) to obtain usage data of the NCI QuitGuide app for our research participants (using de-identified ID numbers), with participants’ explicit permission, as explained in the study facts sheet. We hypothesize that SiS > QG.
- i. *(SiS and QG only)* Self-reported app usage – number of days used app, asked per week; if used, how many minutes per typical day used app
- j. *(SiS and QG only)* Likability rating of the app as measured at end of treatment (i.e., “How much did you like using the smoking cessation app we asked you to use?” 5-point Likert: 1 = I strongly disliked using the app, 2 = I somewhat disliked using the app, 3 = I neither liked nor disliked using the app; 4 = I somewhat liked using the app, and 5 = I strongly liked using the app). We hypothesize that SiS > QG.
- k. *(SiS and QG only)* Satisfaction rating of the smoking cessation support provided by the app (i.e., “How satisfied are you with the smoking cessation support this app provided you with?” 5-point Likert: 1 = very unsatisfied, 2 = somewhat dissatisfied, 3 = neither satisfied nor dissatisfied, 4 = somewhat satisfied, 5 = very satisfied). We hypothesize that SiS > QG.
- l. *(SiS and QG only)* App usability ratings, as assessed via the System Usability Scale (SUS), a simple, ten-item attitude scale giving a global view of subjective assessments of usability, adapted to include language specific to the smoking app (e.g., “I found the smoking app unnecessarily complex” 5-point Likert: 1 = strongly disagree, 5 = strongly agree). We hypothesize that SiS > QG.

3. (exploratory) To test, via mediational modeling, how treatment via the proposed app conferred benefit, or, if not effective, if failure is due to the treatment failing to impact hypothesized mechanisms of change, or because these mechanisms fail to impact outcome. The outcome of interest in these mediational models is self-reported 30-day abstinence at the final follow-up, 6 months post quit. The mediators to be tested, are:
  - a. Self-efficacy as measured via the Smoking Self-Efficacy Questionnaire (SEQ); this is also our primary outcome variable, as described above.
  - b. Emotional well-being
    - i. Positive and negative affect, as measured via the positive affect subscale of the Positive And Negative Affect Schedule (PANAS): For each subscale, both positive and negative, 10 mood adjectives are displayed. Participants rate to what extent they have felt each emotion on a 5-point scale [1 = very slightly or not at all, 5 = extremely]. In this study, the timeframe of reference is the past week.

- ii. Happiness, as measured via two single-item measures, both rated on a 0-100 slider, anchored at 0=not at all, 100=extremely: “In the PAST WEEK, how happy have you felt?”; “How happy are you feeling RIGHT NOW?”
- iii. Satisfaction with life, as measured via the Satisfaction with Life Scale (SWLS): 5 items rated on a 7-point Likert scale [e.g., “In most ways my life is close to my ideal].
- iv. Subjective happiness, as measured via the Subjective Happiness Scale (SHS); 4 items rated on a 7-point Likert scale [e.g., “Some people are generally very happy. They enjoy life regardless of what is going on, getting the most out of everything. To what extent does this characterization describe you?”]).
- v. Stress and Coping, as measured via the stress and coping subscales of the Perceived Stress Scale (PSS10): 10-item self-report scale that measures the degree to which situations in one’s life are appraised as stressful. Items are worded both negatively (e.g., “In the last month, how often have you been upset because of something that happened unexpectedly?”) and positively (e.g., “In the last month, how often have you felt that you were on top of things?”) Traditionally, for a total score, positively worded items are reverse-scored, then sum-scored with the negatively worded items. More recently, the PSS-10 has been conceptualized as assessing two subscales, perceived stress vs. perceived ability to cope with stressors, which is how we will score this scale for this study.

- c. Desire to smoke, as measured via the Brief Questionnaire of Smoking Urges (QSU): a 10-item self-report measure of craving. Sample items include: “I have an urge for a cigarette” and “I would do almost anything for a cigarette now” and are rated on 7-point Likert scale [1 = strongly disagree, 7 = strongly agree]).
- d. Breadth of thought-action-repertoire, as measured via the Modified Twenty Statements Test (MTST): participants list any and all “actions” they can think of while experiencing a specific emotion. We have modified Fredrickson’s scale to make it smoking-specific [e.g., at baseline, it states “Name the strongest emotion you feel when thinking about your upcoming quit attempt. Take a moment to experience that emotion. Concentrate on it and live it as vividly and as deeply as possible. Now recall the most recent cigarettes you have smoked. Given the feeling you just named ([piped]), please list all the things you could have done instead of smoking at those times. You can list as many or as few things as come to mind in the lines below”].
- e. Processing of self-relevant health information
  - i. Perceiving effects of smoking, as measured via the Attitudes Towards Smoking Scale (ATS): an 18-item self-report measure assessing to what degree participants perceive adverse effects of smoking, psychoactive benefits of smoking, and pleasure of smoking.
  - ii. Importance of the pros and cons of smoking, as measured via the Decisional Balance Inventory – short form (DCB) for Smoking: a 6-item scale which rates the perceived importance of pros and cons of smoking.
  - iii. Single item pros (rated on a 0-10 slider scale [0 = not at all, 10 = extremely important]; “Think about all the things you LIKE/LOVE about quitting/being smoke-free; taken together, how important are those things to you RIGHT NOW?”)

- iv. Single item cons (rated on a 0-10 slider scale [0 = not at all, 10 = extremely important]; “Think about all the things you DISLIKE/HATE about quitting/being smoke-free; taken together, how important are those things to you RIGHT NOW?”)
- v. Commitment to Quitting Smoking, as measured via the Commitment to Quitting Smoking scale (CQSS), an 8-item self-report measure capturing the extent to which persons feel personally obligated to persist in quitting smoking despite difficulties, craving and discomfort.
- vi. Single item how motivated (rated on a 0-10 slider scale [0 = not at all, 10 = extremely motivated]; “How MOTIVATED are you to quit smoking/stay quit?”)

### III. SUBJECT SELECTION

Eligibility criteria includes the following: (a) 18+ years of age, (b) smartphone ownership (Android or iPhone only), (c) current nondaily smoker, who smokes at least weekly, and no more than 25 out of the past 30 days, and (d) lifetime history of having smoked 100+ cigarettes, and (e) is willing to make a smoking quit attempt as part of this study (f) currently residing in the United States of America. We will use both grass-root efforts (e.g., PI’s Harvard Scholar website, Craigslist, quit smoking forums) and commercial advertising (e.g., Facebook).

In addition to the aforementioned recruitment methods, we will also recruit through the RPDR (Research Patient Data Registry) at Partners Healthcare. The Research Patient Data Registry (RPDR) is supported by the dedicated team of nearly a dozen developers and support personnel. RPDR is the centralized clinical data registry/warehouse directed by Research IS & Computing’s Director, [name]. PhD. The RPDR gathers data from hospital systems and stores it in one place, bringing clinical information to a researcher’s fingertips and ensuring the security of patient information. We will run bi-weekly queries for current nondaily cigarette smokers seen at Partners Healthcare primary care sites, and subsequently submit the appropriate data requests to receive the following identifiable information: MRN (medical record number), contact information (email address, phone number, and mailing address), and RODY answer (yes/no). We will only contact patients who are designated “yes” in the Epic system, for the column “okay to contact.” Under the new MGB opt-out system, this column designates “whether it is okay to contact the patient about research recruitment. This may be based on the patient’s explicit preference, system default, or an override rule. The information displays in Yes/No format.

In addition to the above mentioned recruitment efforts, research staff will use EPIC to assist in recruitment. To this end, we have worked with the Partners eCare Research Core (PeRC) to set up the necessary steps. PeRC leverages the Epic EHR to assist researchers in identifying and recruiting patients for their research studies conducted at Partners HealthCare. PeRC will put together a report through EPIC based on a list of predetermined variables (please see attached list of variables to be extracted – this list includes contact information and smoking status). After Epic training, and hands-on guidance from the PeRC team, study staff will run this automated report within Epic to identify patients who are smokers and recently completed a primary care visit at MGH. For those who have RODY status = “yes”, study staff will send an opt-out email via Patient Gateway (please see attached letter). (A RODY “yes” designation in Epic means as shown in the report that the patient “okay to contact the patient about research recruitment. This may be based on the patient’s explicit preference, system default, or an override rule.” )For those who do not opt out of hearing about the study, study staff will follow-up by phone to ask about their interest in participating in the study, and, if interested, will phone screen them.

We will use stratified enrollment to ensure that our final sample will (a) be equally balanced between men and women, and (b) reflect national prevalence rates of nondaily smoking in terms of ethnicity and race, where we will enroll no more than 54% non-Hispanic White participants, as per the 2014 National Health Interview Survey ([http://www.cdc.gov/nchs/nhis/nhis\\_2014\\_data\\_release.htm](http://www.cdc.gov/nchs/nhis/nhis_2014_data_release.htm)), which shows that 54% of nondaily smokers are non-Hispanic White.

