(please see attached for the specific check items), staff will inform the screening participant that they are ineligible for the study. If the survey is complete and valid, staff will collect (via email, phone, and/or REDCap form) the contact information for collaterals the participant would like to specify for this study. Social security number (to enable payment by check) and a mailing address to which Accounts Payable can mail the check containing remuneration will be collected via phone, and only after participants have been enrolled in the study. For screen participants who do not enroll in the study (i.e., because they are ineligible or because they decide against the study) study staff will ask for verbal consent (via phone) to allow us to collect their SSN (during the same phone call) and send them a check for completing the screening survey.

At the end of this phone call, study staff will ask the screening participant to indicate the date on which they would like to quit smoking. The enrollment call is then scheduled to occur 8 days before that date. If the chosen quit date falls on a Monday or Sunday, meaning that the enrollment call should be on a Saturday or a Sunday, the enrollment call will be adjusted to fall on a weekday.

During the enrollment call, staff will review the study fact sheet with the participant, and will invite the participant to ask any questions they may have about the study and all its procedures. Once all questions have been answered, study staff will ask the participant to give verbal consent to enroll in this study. The date and time of this verbal consent will be documented by study staff in our REDCap dataset.

After providing verbal consent, the participant is randomized. This is an unblinded study. Randomization will occur via a randomization sheet, as generated using the PROC PLAN procedure in the statistical software package SAS. Randomization will be in a 1:1:1 ratio (SiS3 vs. QG vs. TAU), with a block size of 4. Study staff will use the randomization sheet to determine the participant's treatment group, document this randomized assignment in our REDCap dataset, and will then onboard the participant to the smoking cessation support they have been randomized to receive (i.e., our smartphone app SiS or NCI's app QuitGuide or TAU, which consists of NCI's written materials, "Clearing the Air"), using a time-matched, ~15 minute script.

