**Analytic Plan.** All successfully enrolled participants (i.e., passed the screening process, was successfully onboarded to the assigned smoking cessation materials) will be included in the outcome analyses. For hypotheses only relevant to the SiS and QG conditions (marked in Specific Aims), only participants successfully onboarded to those conditions will be included in the analyses.

1. **Primary Outcome (Aim 1).** In this proof-of-concept RCT, the primary outcome is self-efficacy to abstain from smoking, as measured by the SEQ-12. The primary endpoint is end-of-treatment, which occurs 6 weeks after the originally chosen quit day. To test for differences between randomized groups, we will fit a fixed effects repeated measures model using PROC MIXED, where observations are modeled as nested within persons. Predictors included in the model will be GROUP (i.e., SiS vs. QG vs. TAU), TIME (i.e., BL, Week 2, Week 6, Week 12 and Week 24), and the GROUP\*TIME interaction effect. A contrast statement will be used to derive the test statistic for the GROUP comparison at Week 6, our primary endpoint, given the overall longitudinal model. This contrast statement will test the null hypothesis that SiS = QG = TAU. If this null hypothesis is rejected ( $p<0.05$ ), we will conduct pair-wise follow-up tests that compare the three possible pairwise comparisons (i.e., SiS vs. QG, SiS vs. TAU, and QG vs. TAU).
2. **Secondary Outcomes (Aim 2).** The secondary outcomes in this proof-of-concept RCT are exploratory. Thus, we will not correct for multiple testing. We will fit one model per secondary outcome, using an alpha of 0.05 for all analyses.
  - 2.1. To test for differences between randomized groups for outcomes that are assessed multiple times (Aims 2a, 2b), our overall modeling approach will be the same as for Aim 1. That is, for each outcome, we will fit a fixed effects repeated measures model, where observations are modeled as nested within persons. Predictors included in the model will be GROUP, TIME, and the GROUP\*TIME interaction effect. However, for these secondary outcomes, the definitions of the TIME effect varies across these secondary outcomes, based on their assessment schedule. The distribution of the outcome variables also varies across these variables. Thus, we will implement this overall modeling approach for these variables as follows:

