- 2.2. To test for differences between randomized groups for outcomes that are only assessed at end of treatment (Aims 2c – 2l), for each outcome, we will use a fixed effects model, where GROUP is the only predictor, and score at end of treatment is the dependent variable. Histograms will be used to guide selection of the most appropriate distribution. We anticipate that we will use the normal distribution for the CSQ-8 (Aim 2c), use of strategies (Aim 2e), perceived impact (Aim 2f), the AS (Aim 2g), actual app usage (Aim 2h), self-reported app usage (Aim 2i), likeability of the app (Aim 2j), satisfaction with the app (Aim 2k), and the SUS (Aim 2l), as implemented via the PROC MIXED procedure in SAS. We anticipate that we will use the Poisson distribution for time spent applying content (Aim 2d), as implemented via the PROC GENMOD procedure in SAS. If the GROUP effect is statistically significant ( $p<0.05$ ), we will conduct pair-wise follow-up tests that compare the three possible pairwise comparisons (i.e., SiS vs. QG, SiS vs. TAU, and QG vs. TAU). These follow-up analyses will not be necessary for secondary outcomes that are only assessed for the SiS and QG conditions (i.e., Aims 2j-2l).
3. Exploratory mediational models (Aim 3): We will use mediational modeling, using the product-of-coefficients approach and a fully lagged model to test if hypothesized within-person changes (see Figure 1) occur, and if they are linked to subsequent abstinence. The independent variable will be randomized group assignment (i.e., SiS vs. TAU), and the outcome variable will be self-reported 30-day point prevalence abstinence as measured at 6-month follow-up). The mediators will be our theorized mechanisms of change, as listed in the Aim 3 (i.e., self-efficacy, emotional well-being, desire to smoke, breadth of thought-action-repertoire, processing of processing of self-relevant health information.). Baseline values on these constructs will be included in the model to control for individual differences

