on these measures. The mediator will be scale scores observed at mid-treatment, at the 2-week assessment, which marks the end of the cessation phase. We will use multiple mediation to determine the relative importance of each mechanism, and moderated multiple mediation to identify differences in mechanisms across subgroups (e.g., males vs. females, young adult vs. older adults), similarly to our approach in delineating mechanisms of behavior change in Alcoholics Anonymous.

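### Sex and non-Hispanic White status are set by enrolment quotas and known before randomisation, but the allocation list and the Aim 1 and 2 models do not use them; prespecified adjustment would be a small, nearly free gain

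*Combined protocol and SAP*

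**What the plan says.** **Enrolment.** Section III (Subject Selection) sets quotas for the total sample. For sex: "We will use stratified enrollment to ensure that our final sample will (a) be equally balanced between men and women". For race and ethnicity, so that the sample resembles nondaily smokers nationally: "where we will enroll no more than 54% non-Hispanic White participants".

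**Randomisation.** Section IV (Subject Enrollment) describes a single list: "Randomization will occur via a randomization sheet, as generated using the PROC PLAN procedure" in SAS. It continues: "Randomization will be in a 1:1:1 ratio (SiS3 vs. QG vs. TAU), with a block size of 4". It names no stratification factor.

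**Analysis.** Section VI (Biostatistical Analysis) gives the model terms:
- Aim 1: "Predictors included in the model will be GROUP (i.e., SiS vs. QG vs. TAU), TIME" and their interaction.
- Aims 2a and 2b: "Predictors included in the model will be GROUP, TIME, and the" interaction of the two.
- Aims 2c to 2l: "we will use a fixed effects model, where GROUP is the only predictor".
- Exploratory Aim 3: "moderated multiple mediation to identify differences in mechanisms across subgroups (e.g., males vs. females, young adult vs. older adults". This is the only place where the analysis plan mentions sex. Race and ethnicity appear in no analysis.

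**Timing.** Table 1 in Section V lists demographics, which include gender, ethnicity and race, at baseline. The baseline survey is part of screening, and randomisation follows later, on the enrolment call. Both factors are therefore on file before allocation.

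**The concern.** The sponsor considers sex and non-Hispanic White status important enough to control at enrolment, and has both values in hand before allocation. Neither is then used to allocate participants or to compare arms in Aims 1 and 2.

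Quotas on the total do not fix the split within each arm, so that split is left to chance. If either factor is related to smoking self-efficacy, an uneven split moves the Week 6 comparison, and the variance the factor explains stays in the error term. Nothing else in the Aim 1 model takes this up: baseline self-efficacy enters as one level of TIME in the outcome, not as a covariate, and the contrast compares group means at Week 6.

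At stake are a little precision in the primary comparison and a prespecified answer should the baseline table show a visible imbalance.

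**Working it through.** **1. The plan's own figure.** Section VI gives d = 0.50, 64 per group, 85% retention, 75 enrolled per group and 225 in total. The power paragraph states neither alpha, sidedness nor power. I assume two-sided 0.05 and 80%.
- Exact two-sample t calculation: power is 0.801 at 64 per group and 0.795 at 63. So 64 reproduces.
- 64 / 0.85 = 75.3, stated as 75 (75 × 0.85 = 63.75). Close enough.

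**2. Inputs for arm balance.** N = 225, n = 75 per arm. Women: 112 of 225. Non-Hispanic White: 0.54 × 225 = 121.5, taken as 121. I assume that the quotas are met exactly, that the arms are exactly 75 each, and that allocation takes no account of either factor.

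**3. Spread of the difference between two given arms.** For a factor with overall share p,

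SD = √[ p(1 − p) × (2/n) × N/(N − 1) ].

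For women: √(0.25 × 2/75 × 225/224) = 0.082, or about 8 percentage points. About 95% of absolute differences lie within 1.96 × 8.2 = 16 points.

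**4. Chance of a visible gap.** Simulation of 200,000 unstratified allocations:

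| Gap in share | A given pair, women | Widest of three pairs, women | A given pair, non-Hispanic White | Widest of three pairs, non-Hispanic White |
|---|---|---|---|---|
| ≥ 10 points | 22% | 44% | 22% | 44% |
| ≥ 15 points | 6% | 15% | 6% | 15% |
| ≥ 20 points | 2% | 5% | 2% | 5% |

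For comparison, with permuted blocks inside the four cells of sex by non-Hispanic White status, the largest gap in 20,000 simulated trials was about 2 points (blocks of 3) or 4 points (blocks of 6).

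**5. Effect on the contrast.** Shift = gap × difference in self-efficacy between the factor's two levels. The documents give no such difference, so I assume 0.2 to 0.5 SD.
- 10-point gap: 0.10 × 0.2 = 0.02 SD to 0.10 × 0.5 = 0.05 SD.
- 16-point gap: 0.16 × 0.2 = 0.03 SD to 0.16 × 0.5 = 0.08 SD.

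For scale, the design effect is 0.50 SD, and the standard error of a two-arm difference with 64 per arm is √(2/64) = 0.18 SD.

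**6. Gain from adjustment.** A factor split 50:50 with effect b explains 0.25 × b² of the variance: 0.01 at b = 0.2 and 0.0625 at b = 0.5. Dividing d by the remaining SD gives 0.50/√0.99 = 0.503 and 0.50/√0.9375 = 0.516. With 64 per group, power goes from 0.801 to 0.805 and 0.826. These figures are for one factor and one pairwise comparison.

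**The case against.** The strongest reply is that nothing here is wrong. The quotas have a stated purpose, which is the make-up of the total sample, and the race rule is a cap rather than a set of strata. Nowhere do the documents promise balance between arms. Unstratified randomisation is valid, chance imbalance is already allowed for in the test's error rate, and a model need not carry factors that the randomisation did not use. All of this stands.

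A reader might go further than the documents allow in four ways.
- *That the quotas do nothing for the comparison of arms.* An equal split in the total gives the smaller sex the largest expected number in each arm, which helps the Aim 3 comparison of men and women.
- *That this Aim 3 analysis needs sex to be evenly spread over arms.* It needs adequate cells, not equal ones. With 44 women in one arm and 31 in the other (a 17-point gap) and the reverse in men, the variance of the sex-by-arm contrast rises by a factor of (2/44 + 2/31)/(4/37.5) = 1.03. The standard error therefore rises by about 1.5%.
- *That every outcome analysis ignores both factors.* That is true of Aims 1 and 2 only, since Aim 3 names sex as a possible moderator. In Aim 2b the outcome is change from baseline, so a stable difference in cigarette level between the sexes would largely cancel.
- *That the 44% figure measures the risk to the main comparison.* It takes the widest of three pairs at an arbitrary threshold. For one named pair, such as SiS against TAU, the figure is 22%.

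The benefit also rests wholly on an assumed prognostic effect. If neither factor predicts self-efficacy, there is almost nothing to gain.

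**Conclusion.** The point holds as a minor, optional improvement. Two factors that the sponsor already manages, and knows before allocation, are unused in the randomisation and in the Aim 1 and Aim 2 models. This is not a bias, an invalid design or a contradiction between sections.

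Imbalance of 10 points or more between two given arms is fairly common (about 22% of trials), but its likely effect on the primary contrast is small: 0.02 to 0.05 SD if the factor is worth 0.2 to 0.5 SD. Power for one pairwise comparison would rise by 0.004 to 0.025. These sizes rest on the assumed prognostic range, on exactly 75 per arm, on quotas met in full, and on the assumed two-sided 5% level. The case for acting is that adjustment costs almost nothing and settles in advance how a visible baseline imbalance would be handled.

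**What to change.** Before outcome data are examined, add sex and non-Hispanic White status as prespecified fixed effects in the Aim 1 PROC MIXED model. State whether they enter as main effects only, which assumes the same difference at every visit, or also with TIME.

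If wanted, add the same two terms to the linear Aim 2 models. For the Aim 2a logit model, note that an adjusted odds ratio is conditional on the covariates and is not the same quantity as the unadjusted one.

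Stratifying the list by sex is optional, and only if randomisation has not begun; the documents do not say whether it has. Because staff read assignments from a sheet, separate lists add a step of choosing the right list. Whether a block of 4 can serve three arms equally is a separate matter, and this point does not rest on it.

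The cost is two extra model terms, with no new data and no more participants. The downside is a negligible gain if the factors turn out not to be prognostic.
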